5.8 Packaging

The study medications will be dispensed in sterile eye droppers of 3 ml volume, which will be used as single-dose applications. One drop of the placebo/ drug solution will be administered to each eye. Therefore 2 eye droppers will be required per day because the placebo/drug is administered two times a day. At each visit, subjects will receive 56 sterile eye droppers that will be used as single-dose applications. The eye droppers will be placed in a dark (brown) colored packet before being dispensed to the subject. A label with abbreviated information will be placed on each eye dropper. The zip-lock packet will include the subject's name, stage of visit, instructions for drug use and storage and the drug expiration date. The label will also include the study name (abbreviated) and a statement that the drug is **investigational** for use only in this research study." The first dose will be administered to the subject by the researcher from one of the eye droppers that will be dispensed to the subject at the first treatment visit (visit 2, day 1). No separate packing will be done for the study medication to be used in the MD's office. The subjects will receive the 4 weeks of remaining doses in a dark packet to take home. 56 sterile eye droppers will be dispensed at each visit.

5.9 Receiving, Storage, Dispensing and Return

5.9.1 Receipt of Drug Supplies

The UIC Investigational Drug Service (IDS) or EEI Pharmacy will order the study drug. The study drug will be stored in the Taylor Street/ EEI pharmacy and dispensed to subjects as needed.

5.9.2 Storage

Study medication will be stored at EEI pharmacy until such time as a subject visit is scheduled. The study medication will be directly dispensed to the subject from the EEI pharmacy on each treatment

visit, except for the first dose that is administered in the clinic under the supervision of research personnel. The study medication will not be stored in the MD's office, except when a subject receives his/her first dose, when the medication may be kept in the MD's office at room temp, away from direct strong light.

5.9.3 Dispensing of Study Drug

At the first treatment visit (day 1), the first study medication dose will be administered to the subject in the clinic and eye droppers sufficient to last for 4 weeks will be given to them to take home. The subjects will be asked to return the used and unused eye droppers at the follow-up visits. We will then retrieve the previously -dispensed eye droppers and a fresh 4 week supply will be dispensed by the pharmacy. This will be done at first treatment visit (day 1) and week 4. No new drug eye droppers will be given on the week 8 visit.

5.9.4 Return or Destruction of Study Drug

At the completion of the study, there will be a final reconciliation of drug ordered/ received, drug consumed, and drug remaining. Any discrepancies will be investigated, resolved, and documented. The used drug eye droppers will finally be disposed by the pharmacy according to the pharmacy standard protocols.

6 Study Procedures

6.1 Subject Recruitment and Screening

Prior to recruitment of any subjects into the study, written approval of the protocol and informed consent will be obtained from the Institutional Review Board (IRB).

Potential subjects will be recruited from the clinical practice of the principal investigator (PI) at the time of their routine eye examination visit. The clinical practice is located at the Department of Ophthalmology and Visual Sciences, Eye and Ear Infirmary, [name]. Subjects will include patients who have been diagnosed with dry eye in the investigator's eye clinic (cornea clinic or the comprehensive eye clinic), in the Illinois Eye and Ear Infirmary. Patients may also be referred to the PI's clinic by other Ophthalmology physicians at UIC, as well as the Ophthalmology departments at Loyola University Chicago, University of Chicago, RUSH University, Cook County Hospital, and Northwestern University. These centers will be provided with 'information sheets' to provide to subjects before they come to the PI's clinic. The referring physicians shall inform the patients briefly about the study and provide them with the information sheet (enclosed), but no study related procedures (including screening and recruitment) will be performed at any location outside the PI's clinic at UIC (Illinois Eye and Ear Infirmary). Even the patients referred to the PI's clinic for possible enrollment in the study, will be screened and, if eligible, recruited in the study only at the PI's clinic. The information sheet that will be given to the subjects are attached.

Patients with established Dry Eye Disease (for at least 6 months, with Schirmer's test ≥ 0 to ≤ 9 mm/5min and annoying or activity limiting visual symptoms) will be approached by a member of the research staff to determine if the patient might be interested in participating in a research study. If the subject is interested, the research staff member will describe the study. If the subject is willing to enter the study, the subject will be asked to review the study consent form, the PI will meet with the subject to review the form, the study will be discussed to conform the subject's understanding of the study, and to answer any questions that the subject might have. Once the subject demonstrates understanding of the study and agrees to participate in the study, the subject will be asked to sign the informed consent form

in the presence of the PI. Patients that contact the researchers in response to a flyer and information sheet provided by their physician will be scheduled for a visit to discuss the study and participate in the consent process. Consent will be obtained prior to screening to determine eligibility. Subjects will be screened for eligibility, as per the inclusion/ exclusion criteria, and as detailed in section 6.5.1. Eligible subjects will be enrolled in the study.

6.2 Assignment of Subject Identification

A study identification (ID) number will be assigned to each subject at screening. This study ID number will be used on all study-related documents. To maintain confidentiality, the subject's name will not be recorded on any study document other than the informed consent form. The master code list will link the subject MRN to the study ID number given to each subject. The master code list will be stored on password protected desktop in PI's OFFICE in Lions of Illinois Eye Research Institute (LIERI). The data collected and master code list will be accessible only to the PI and the research team involved in this project. The desktops will be password protected as well. Data will not be shared over the internet and will remain password protected. Confidentiality will be maintained. Data will be de-identified post publication of the study results and for subjects determined to not meet eligibility criteria or who later decline participation in the consent process.

6.3 Screen Failure

A record of screen failures and the reasons for non-eligibility to the study will be maintained.

6.4 Subject Enrollment

Subjects meeting the enrollment criteria (see Sections 4.1) will be eligible for the study.

6.5 Study Assessments

The following detailed procedures are performed at the designated clinic visit. All results will be documented on the subject's medical/research charts, source documents, and CRFs as required. All ophthalmic procedures will be performed on both eyes.

6.5.1 Visit 1 Screening

Day -21 to 0

After obtaining informed consent, the following assessments will be performed within fourteen days prior to the subject receiving the first dose of study medication:

- Demographic information including: birth date, gender, race or ethnic origin.
- Medical History including prior medication use and prior procedures: Medical history will be obtained by interviewing the subject and will include a review of the following systems: cardiovascular, dermatologic, gastrointestinal, genitourinary, musculoskeletal, neurologic and respiratory. An allergic history (including medications and food), substance abuse history (including alcohol) and a history of medication use (including prescription, OTC, and herbal products) during the past 30 days will also be completed.
- Ophthalmic and Dry Eye Disease history including: date when the Dry Eye Disease began, verification that the subject has had Dry Eye Disease for at least 6 months, medications used by the subject to treat Dry Eye Disease, previous procedures to treat Dry Eye Disease.

- Ophthalmic Examination (slit lamp examination, Ocular Surface Redness Score, Ocular Surface Disease Index, Lissamine Dye staining, and a Schirmer I test)
- Pregnancy test, if applicable. Women of reproductive age will be asked to use a method of birth control that is acceptable to the subject and the study doctor. This may include oral contraceptive pills, birth control implants/shots or patches, barrier methods or abstinence. Women of reproductive age will not be included in the study if they refuse to use any birth control measure, including abstinence.

Subjects currently treating DED with corticosteroids and/or Restasis will continue these treatments during the whole study. If patients are wearing contact lenses (Soft bandage contact lenses or PROSE lens) or using serum tears, they will be asked to discontinue contact lens wear or use of serum tears for 2-weeks prior to being enrolled (Baseline visit) and will be required to not wear contact lenses or use serum tears for the duration of the study (until week 10 visit). The study doctor will provide advice about decreasing DED symptoms with artificial tears, eyelid massage, or warm compresses.

If the subject agrees to enter the study after screening, the “Visit 2 Day 1 (Randomization and First treatment visit)” will be scheduled. Visit 2 can be scheduled any time in the next 2 weeks after the screening visit. If a subject wears contact lenses or uses serum tears and wants to participate in the study, then they will be asked to discontinue the use of contact lenses or use of serum tears and a washout period of 2-weeks (± 2 days) will be needed before baseline visit (Visit 2).

In some subjects, detailed screening may not have to be performed as the subjects may have been followed and treated for Dry Eye in the PI’s clinic. In these cases, some or all of the screening test may have been performed during the subject’s routine dry eye care. These subjects will not be screened formally. An informed consent will be administered and subjects will be given an appointment for baseline visit examination.

6.5.2 Visit 2 Day 1 (Randomization and First treatment visit)

Prior to first dose (Baseline)

- Record concomitant medications
 - Vital Signs: Blood pressure, Pulse, and Temperature taken while subject is in a sitting position.
 - Visual Acuity (Snellen’s chart) with eye glasses (if applicable)
 - OSDI
 - Symptom Intensity Assessment
 - Keratograph Oculus Redness Score
 - > Non-invasive Keratography Tear Film Break-up Time (NIK BUT)
 - Schirmer I test
 - Baseline Ophthalmic Examination (slit lamp examination, VBR)
 - Ocular surface wash collection for analysis (Potential biomarkers)
 - InflammADry Test for MMP-9 Protein
 - Lissamine Dye Corneal and Conjunctival staining
 - Adverse events since screening visit.
- ***Randomization (by pharmacy)***
 - ***Dispensing of study drug/placebo (by Pharmacy)***
 - ***Investigator/designee administers first dose of study drug/ placebo***

Post-Dose

- Test Substance Tolerance (Visual Analogue Scale; VAS)
- Subjects will be trained on how to self-administer the study eye drops and be given a sufficient supply to last for 4 weeks to take home.
- Subjects will receive a study diary on which to record the day/time of each dose and any adverse effects.
- Post dose evaluation for any adverse effects.
- Intraocular pressure measurement after topical anesthesia to eye

6.5.3 Visit 3: Week 4 (\pm 4 days)

Treatment Visit (after any dose for that day)

- Review the subject's diary and record changes in concomitant medication, deviations from drug schedule and adverse events.
- Vital Signs: Blood pressure, Pulse, and Temperature taken while subject is in a sitting position.
- Visual Acuity (Snellen's chart) with eye glasses (if applicable)
- OSDI
- Symptom Intensity Assessment, SGA and CGA
- Test Substance Tolerance (VAS)
- Baseline Ophthalmic Examination (slit lamp examination, VBR)
- *Dispensing of study drug/placebo (by Pharmacy to patient)*
- *Returning of unused study drug/ placebo (by patient to pharmacy)*

6.5.4 Visit 4: Week 8 (\pm 4 days)

Treatment Visit (after any dose for that day)

- Review the subject's diary and record changes in concomitant medication, deviations from drug schedule and adverse events.
- Vital Signs: Blood pressure, Pulse, and Temperature taken while subject is in a sitting position.
- Visual Acuity (Snellen's chart) with eye glasses (if applicable)
- OSDI
- Symptom Intensity Assessment, SGA and CGA
- Test Substance Tolerance (VAS)
- Keratograph Oculus Redness Score
- > Non-invasive Keratography Tear Film Break-up Time (NIK BUT)
- Schirmer I test
- Baseline Ophthalmic Examination (slit lamp examination, VBR)
- Ocular surface wash collection for analysis (Potential biomarkers)
- InflammDry Test for MMP-9 Protein
- Lissamine Dye Corneal and Conjunctival staining
- Intraocular pressure measurement after topical anesthesia to eye
- **Returning of unused study drug/ placebo (by patient to pharmacy)**

6.5.5 Visit 5: Week 10 (\pm 4 days)

Follow-Up Visit

- Review the subject's diary and record changes in concomitant medication and adverse events.
- Vital Signs: Blood pressure, Pulse, and Temperature taken while subject is in a sitting position.
- Visual Acuity (Snellen's chart) with eye glasses (if applicable)
- OSDI
- Symptom Intensity Assessment, SGA and CGA
- Baseline Ophthalmic Examination (slit lamp examination, VBR)

- **Returning of patient diary (by patient to PI)**

7 Statistical Plan

7.1 Sample Size Determination

As this is a feasibility trial intended to guide the planning of larger future investigations, there are no formal sample size calculations.⁶⁵ The aim of the study is to recruit a sufficient number of patients to evaluate the acceptability and safety of the intervention and the study design. An outcome of this study will be to estimate parameters such as the SD for a sample size calculation of a subsequent full-scale trial. A sample of 24 patients (12 in each arm) is considered adequate for obtaining reliable sample size estimates.^{66, 67} To allow for a conservative attrition rate of 10%, we aim to recruit 28 patients into the trial.

7.2 Statistical Methods

Based on the classification of reasons for conducting pilot studies by Thabane et al, in this pilot study we will assess the following: (i) Process– recruitment rate, retention rate, (non)compliance or adherence rate; and (ii) Scientific– safety (adverse event/SAE rate), tolerability, and efficacy, including reduction in clinical signs and symptoms (OSDI, Corneal staining, Redness etc as detailed in section 3.4) and treatment effect size. We will calculate the observed rate with 95% confidence interval for each rate by treatment group. Other descriptive statistics, including median with interquartile or mean with standard deviation for continuous variables and frequency with percentage for categorical variables will be reported as well. To estimate the preliminary efficacy under the scientific category, one eye (target eye) will be selected at screening visit as follows: (i) if only 1 eye meets inclusion criteria, this eye is used; (ii) if both eyes meet inclusion criteria, the eye with the higher corneal stain score is used; (iii) if both eyes have the same corneal stain score, then the one with the lower Schirmer I score is used; (iv) if both eyes have same scores, the right eye is used. Secondary analyses will be performed for the non-target eye as well. Due to the nature of this feasibility study, any efficacy statistical tests and adjusted analyses will not be conducted. Detailed data validation will examine completeness, existence and accuracy of collected data to assess data quality and identify missing and conflicting data. Statistical analysis will be performed on an intention-to-treat basis i.e., inclusion of all patients randomly assigned, regardless of adherence, actual treatment received, and subsequent withdrawal of treatment and/or deviation from the protocol and per-protocol (i.e., inclusion of those who completed the treatment as planned) and will be reported according to 2010 CONSORT guidelines. All statistical analyses will be completed using SPSS Statistics V.22.0.31

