3.1 General Design

This will be a Randomized controlled trial, in which a total of 28 subjects will be enrolled at 1 clinical site. Subjects will be randomly assigned to one of two groups (#1, #2), with 14 subjects per group. One group will be given placebo (Normal saline eye drops) and the other group will be given eye drops containing the study drug (IVIG).

Patients with established Dry Eye Disease will be approached by a member of the research staff to determine if he/ she might be interested in participating in a research study. If the subject is interested, the research staff member will describe the study. If the subject is willing to enter the study, the study will be discussed and the subject will be asked to sign the informed consent form. Consent will be obtained prior to screening to determine eligibility. Screening procedures include documentation of Dry Eye Disease. Eligible subjects will be enrolled in the study.

All enrolled subjects will receive their first dose of test medication (placebo/ study drug) on study Day 1 in the doctor's office, and after completion of the study assessments, will have the topical eye drops dispensed for self-administration. See Section 5.4 *Preparation and Administration of Study Drug* for details.

Subjects will be provided with diaries to record the time of each dose and will also be asked to record any adverse symptoms. In addition, they will be asked to make a note of any missed doses together with the reason for the omission. Subjects will return at 4 weeks for further study assessments,

thereafter at 8 weeks (the last day of treatment), and again at 10 weeks after two weeks of no treatment with study drug for the final study assessments.

There is no primary efficacy endpoint in this study. Instead several exploratory efficacy endpoints will be assessed.

The primary tolerability endpoint is the change in the test substance tolerance between Day 1 (post-dose) and 8 weeks (56 days).

[figure not shown]

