3.5 Safety Endpoints

Safety assessments include Vital Signs, recording of all complications and adverse events, as well as ophthalmic exam findings. All ocular and non-ocular adverse events will be assessed for severity and relationship to the investigational product.

In addition to the primary tolerability endpoint (Section 2.2), the following safety endpoints will be assessed:

- The proportion of screened subjects who are successfully recruited in the study (i.e., recruitment rate)
- The proportion of eligible subjects at Day 56 who successfully complete (i.e., retention rate, (non)compliance or adherence rate) a full eight weeks (i.e., 56 days) of therapy with topical administration two times per day (BID).
- All reported adverse events, classified by frequency, severity, and relatedness, from baseline (Day 1) through the last study visit (Day 70).
- Clinically significant changes in vital signs or ophthalmic examination from baseline.

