5.3 Method for Assigning Subjects to Treatment Groups

This Randomized placebo-controlled trial will have two study groups. Subjects will be randomly assigned to one of two groups (#1, #2). One group will receive the study drug (IVIg 4mg/ml; test group), and the other group will receive placebo (Normal saline; control group). We will use a computer-based random code generator (Research Randomizer; <http://randomizer.org/>) to generate 1 set of 24 non-unique, unsorted numbers with a range from 1 to 2 representing the group number (#1/ #2). Each subject will be assigned a study identification (ID) number at screening, e.g. Subject #1, subject #2, and subject #3 and so on. Based on the randomizer generated table, subject #1 will receive either placebo or study drug. This will be repeated for each subject. For reproducibility purpose, we will document the final randomization schedule and the random SEED number used to generate the schedule. Randomization will be performed by the Illinois Eye and Ear Infirmary's pharmacy, and neither participants nor research staff will be aware of the assigned treatments. The person conducting the randomization will remain masked as well.

The study identification (ID) number will be used on all study-related documents. The drug vial number will be linked to the subject identification number.

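### Section 7.2 gives process rates and their 95% intervals by arm only: retention and adherence lose precision that pooling would give, and the recruitment rate cannot be split by arm at all

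*Combined protocol and SAP*

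**What the plan says.** Section 7.2 lists the process outcomes as "recruitment rate, retention rate, (non)compliance or adherence rate", adds safety outcomes (adverse event and SAE rates), and then states the rule: "We will calculate the observed rate with 95% confidence interval for each rate by treatment group". The synopsis repeats it. Section 7.2 names the software (SPSS) but no interval method. Neither 7.2 nor 7.3 plans an interval over both arms.

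Two other sections treat the same quantities as overall figures:

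- Section 3.5 (Safety Endpoints) defines retention/adherence without reference to arm: "The proportion of eligible subjects at Day 56 who successfully complete (i.e., retention rate, (non)compliance or adherence rate) a full eight weeks" of twice-daily treatment. It defines the recruitment rate as the share of screened subjects who are recruited.
- Section 7.1 (Sample Size Determination) says the trial is meant to guide larger studies and applies one attrition rate to the whole sample: "To allow for a conservative attrition rate of 10%, we aim to recruit 28 patients into the trial".

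**The concern.** Retention and adherence are the numbers a later trial would use to inflate its sample size. That calculation normally takes one rate, as section 7.1 does here. Giving each rate an interval on 12 to 14 subjects, and none on all randomised subjects, makes the planning figure less precise than the data allow.

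For the recruitment rate the rule cannot be carried out. Screen failures are never assigned to an arm, so there is no by-arm denominator.

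A lesser matter is that the interval method is left open. With arms this small and rates that may lie near 0 or 1, the choice of method can change the reported interval a great deal.

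**Working it through.** **Inputs**

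- Target of 24 evaluable, 12 per arm (7.1: "A sample of 24 patients (12 in each arm) is considered adequate for obtaining reliable sample size estimates").
- Attrition 10%, 28 recruited (7.1).
- Allocation "with 14 subjects per group" (3.1).
- Intervals at 95%, by arm, method not named (7.2).
- Assumed here, because the documents give no expected safety event rate: true rates of 5% and 10% for the check on interval method.

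**1. The plan's own figure.** Inflating per arm: 12 / (1 − 0.10) = 13.3, rounded up to 14, and 2 × 14 = 28. The stated 28 reproduces. (Inflating the total gives 24 / 0.90 = 26.7, or 27.)

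**2. One arm against both arms, same observed proportion lost.** The Clopper-Pearson limits for x of n are the 2.5% quantile of Beta(x, n − x + 1) and the 97.5% quantile of Beta(x + 1, n − x).

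| Lost per arm | One arm (n = 14) | Both arms (n = 28) | Width ratio |
|---|---|---|---|
| 0 | 0 to 23.2% | 0 to 12.3% | 23.2 / 12.3 = 1.88 |
| 1 | 0.2 to 33.9% | 0.9 to 23.5% | 33.7 / 22.6 = 1.49 |
| 2 | 1.8 to 42.8% | 4.0 to 32.7% | 41.0 / 28.6 = 1.43 |

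Wilson gives ratios of 1.78, 1.46 and 1.39 for the same rows. With three or more losses per arm the ratio is 1.34 to 1.41 across the two methods. The large-sample value is √2 = 1.41.

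**3. Average over the outcomes that could occur.** The width is weighted by the binomial probability of each count at the plan's 10% loss.

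- Clopper-Pearson: 35.3 points (n = 14) against 24.4 points (n = 28), ratio 1.45.
- Wilson: 31.4 against 22.3 points, ratio 1.41.
- With 12 and 24 in place of 14 and 28, the ratios are again 1.45 and 1.41.

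**4. Recruitment rate.** The numerator is subjects recruited and the denominator is subjects screened (3.5). Those who fail screening are not randomised, so the denominator cannot be divided between arms.

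**5. Interval method.** The normal-approximation interval is p ± 1.96 √(p(1 − p)/n).

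- With 0 of 14, p(1 − p) = 0 and the interval is 0% to 0%. The exact interval is 0 to 23.2%.
- With 13 of 14 retained it is 79.4% to 106.3%. The exact interval is 66.1% to 99.8%.
- Its true coverage at n = 14, by enumeration, is 51% at an assumed rate of 5% and 76% at 10%. The exact interval covers 99.6% and 99.1%.
- The chance of no event in an arm of 14 is 0.95^14 = 49% at 5% and 0.90^14 = 23% at 10%.
- Pooling does not cure this: 0 of 28 also gives 0% to 0%.

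**The case against.** **No information is lost.** Both arm counts will be reported, so anyone can add them and compute a pooled interval. Section 7.2 also promises frequencies and percentages without restricting them to arms. This stands: a reader might infer that an overall retention figure can never be obtained, and the documents do not support that. What is missing is a planned overall estimate with its interval.

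**By-arm reporting is defensible.** Safety and tolerability of a first topical use is the main objective, and loss may differ between drug and placebo. No progression threshold for retention or adherence is stated, so no decision in the protocol turns on the wider interval. This also stands, and it is why the by-arm rates should stay beside the pooled one. It does not help the recruitment rate.

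**The normal approximation is hypothetical.** A reader might infer that the safety intervals will be far too narrow or will read 0% to 0%. Nothing in the documents selects that method. The collapse needs both that method and zero events, and for retention itself it would read 100% to 100%. The documents give no expected SAE or ocular reaction rate, and the primary tolerability endpoint is a change on a visual analogue scale, which this does not touch. The method is therefore only a detail to fill in.

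**The denominators are not secure.** The synopsis gives 24 subjects, and section 5.3 will "generate 1 set of 24 non-unique, unsorted numbers with a range from 1 to 2", which fixes neither 28 randomised nor equal arms. This is true, but the ratio barely changes at 12 and 24.

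**Adherence is not separately defined.** Section 3.5 runs together "retention rate, (non)compliance or adherence rate" with no adherence cut-off. Pooling does not repair that.

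**Conclusion.** The point holds as a minor reporting matter. Section 7.2 schedules process-rate intervals by arm only, which does not match the single proportion in 3.5 or the single attrition rate in 7.1, and it asks for a by-arm recruitment rate that cannot exist.

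The loss of precision is a factor of about 1.45 in expected exact-interval width (1.41 with Wilson). This assumes equal arms of 14, the plan's 10% loss and the same true rate in both arms. The factor depends on the losses seen: 1.49 with one per arm, near 1.4 with more, and 1.88 with none. A flat statement of 1.5 times would describe one scenario only.

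The unnamed interval method is worth settling but does not carry the point.

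**What to change.** In section 7.2, and in the matching synopsis sentence:

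1. Report retention and adherence with 95% intervals over all randomised subjects as the headline process figures, with the by-arm rates beside them.
2. Report the recruitment rate overall only.
3. Keep AE and SAE rates by arm.
4. As a minor addition, name Clopper-Pearson or Wilson for every interval on a proportion.

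The cost is a few sentences, with no change to visits, data collection or sample size. The pooled rate averages over any real difference between arms, which the by-arm rates still show. Exact intervals will be wider than normal-approximation ones when events are few.

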3.4 Exploratory Study Endpoints

The exploratory study endpoints will include:

1. The change in the Ocular Surface Disease Index (OSDI) which is a patient’s subjective rating scale
2. Change in tear secretion as measured by Schirmer I test
3. The proportion of eyes achieving complete corneal staining clearance after treatment
4. Change in corneal staining score as measured by Lissamine dye staining

[figure not shown]
5. The change in subjective ocular surface redness score (OR) using the validated bulbar redness (VBR) grading scale
6. Visual acuity change
7. Change in frequency of administration of artificial tears or concomitant eye drops
8. Change in number of corneal filaments (slit-lamp examination)
9. Change in amount of mucoid films (slit-lamp examination)
10. Clinical Global Impression (CGI) of change in symptoms from baseline (physician's rating)
11. Subject Global Assessment (SGA) of overall change from baseline (subject's rating)
12. Change in Non-Invasive Keratograph Tear Break-Up Time (NIK BUT)
13. Change in Keratograph Ocular Bulbar Redness Score
14. Change in MMP-9 Protein Detection
15. Change in amount of Cytokines in ocular surface wash

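### Section 7.2 promises a treatment effect size without defining a between-arm contrast or interval and bars baseline adjustment; corneal clearance (endpoint 3) lacks a baseline condition and a missing-score rule

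*Combined protocol and SAP*

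**What the plan says.** Section 7.2 lists efficacy and a treatment effect size among the scientific outputs. The only interval it plans is this: "We will calculate the observed rate with 95% confidence interval for each rate by treatment group". Continuous endpoints are summarised descriptively, "including median with interquartile or mean with standard deviation for continuous variables", so a median alone satisfies the plan. It then states that "any efficacy statistical tests and adjusted analyses will not be conducted", and gives the feasibility nature of the study as the reason.

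Section 7.1 sets the purpose of the numbers: "An outcome of this study will be to estimate parameters such as the SD for a sample size calculation of a subsequent full-scale trial". Section 2 adds that the trial should estimate effectiveness to inform a definitive trial. Section 1.5 says the results will decide which sign or symptom becomes the later primary endpoint. Section 3.1 is clear that "There is no primary efficacy endpoint in this study".

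Endpoint 3 in Section 3.4 is "The proportion of eyes achieving complete corneal staining clearance after treatment". No baseline score, visit or missing-score rule is attached. For the choice of target eye, Section 7.2 says "if only 1 eye meets inclusion criteria, this eye is used". If both eyes qualify, the one with the higher corneal score is taken. It also says "Secondary analyses will be performed for the non-target eye as well".

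**The concern.** The SD and the effect estimate are what this pilot hands to the next trial. If the contrast and its interval are not defined, the report may give point differences on some fifteen exploratory endpoints with no statement of their precision, and Section 1.5 intends to choose among those endpoints. The Day 1 values that could tighten the contrast are collected, yet the plan rules out using them.

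For endpoint 3, two analysts with the same data could report different proportions. An eye that starts at corneal score 0 and stays there could be counted as cleared, as not cleared, or left out. An eye with no week-8 score raises the same three choices.

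**Working it through.** **The plan's own figure.** Section 7.1 wants 12 per arm after 10% attrition: 12/0.90 = 13.3, rounded up to 14 per arm, or 28 in total. This reproduces. The plan gives no SD, correlation or effect size, so the correlation r below is an assumption, with a range shown.

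**Precision of the between-arm difference.** Units are the week-8 SD, with equal SDs at both visits and 12 per arm (N = 24). Here t(0.975, 22) = 2.074, t(0.975, 21) = 2.080 and sqrt(2/12) = 0.408.

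- Week-8 difference, unadjusted: 2.074 × 0.408 = 0.85 at any r.
- Change score: 0.847 × sqrt(2(1 − r)).
- Adjusted for Day 1: 2.080 × 0.408 × sqrt((1 − r²) × 21/20), where 21/20 = (N − 3)/(N − 4) is the cost of estimating the slope.

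| r (assumed) | Week 8 only | Change | Adjusted | Gain over the better unadjusted option |
|---|---|---|---|---|
| 0.3 | 0.85 | 1.00 | 0.83 | 0.847 to 0.830, about 2% |
| 0.5 | 0.85 | 0.85 | 0.75 | 0.847 to 0.753, about 11% |
| 0.7 | 0.85 | 0.66 | 0.62 | 0.656 to 0.621, about 5% |

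Adjusted and change-score variances are equal where 1.05(1 − r²) = 2(1 − r), that is r = 2/1.05 − 1 = 0.905. Above about 0.90 the gain is gone.

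**Can a reader rebuild the adjusted interval?** Sometimes. Within an arm, the covariance of the Day 1 and week-8 values is (SD²Day 1 + SD²week 8 − SD²change)/2. With the sample sizes and both means by arm, on the same subjects, this fixes the common slope, the adjusted difference and its standard error. So all three SDs are needed by arm. Section 7.2 does not require them, and where it permits a median with interquartile range, the route is closed.

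**Can an analysed eye have corneal score 0 on Day 1?** Yes.

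- In Section 4.1, item 3, corneal staining is one of nine alternatives (a to i). Two signs, or a sign and a symptom, are enough.
- The staining criterion in the Study Summary refers to the ocular surface, so conjunctival staining can meet it.
- A sole qualifying eye is the target whatever its corneal score, and the non-target eye is analysed too.
- The target eye is chosen at screening, whereas the pre-treatment baseline is Day 1.

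The documents do not show how often this will happen.

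*Illustration with assumed counts:* 12 eyes in an arm, 4 stained eyes clear, and unstained eyes stay at 0.

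| Unstained on Day 1 | Counted as not cleared | Excluded | Counted as cleared |
|---|---|---|---|
| 0 | 4/12 = 33% | 33% | 33% |
| 1 | 4/12 = 33% | 4/11 = 36% | 5/12 = 42% |
| 2 | 4/12 = 33% | 4/10 = 40% | 6/12 = 50% |

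**Can a week-8 corneal score be missing by design?** Yes, for some subjects. The Schedule of Visits and Section 6.5.4 place the only lissamine staining after Day 1 at week 8. Section 4.4.2 asks those who withdraw earlier for the week-10 procedures plus the tolerance scale, and Section 6.5.5 has no lissamine staining. Section 7.3 keeps these subjects in the intention-to-treat set. Section 7.2 says missing data will be identified but not how they will be handled.

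*Illustration with assumed counts:* 14 randomised to an arm, 2 scores missing, 6 observed clearances. The proportion is 6/14 = 43% (missing as not cleared), 6/12 = 50% (excluded) or 8/14 = 57% (missing as cleared).

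**What a between-arm interval would show.** For an assumed 6/12 versus 3/12, the difference is +25 points, with a Newcombe 95% interval of −12 to +54.

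**The case against.** The plan's choice is deliberate and reasoned. In a feasibility trial with no primary efficacy endpoint, descriptive summaries are acceptable, and reporting means with SDs already supplies an SD for planning. The gain from adjustment is modest. Comparing it only with change scores at r = 0.3 (1.00 against 0.83) would flatter it, because the plain week-8 difference is already at 0.85. More intervals also invite over-reading. With eight independent intervals and no true effect, the chance that at least one excludes zero is 1 − 0.95^8 = 34%. With sixteen, as when the same eight are repeated in the per-protocol set, it is 1 − 0.95^16 = 56%. These objections stand. They limit the point to estimation without tests, on a short list fixed in advance.

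For endpoint 3, achieving clearance naturally suggests prior staining, and when both eyes qualify the more stained cornea is chosen. Both make zero-score eyes less of a problem, but neither is a rule, and neither covers a sole qualifying eye or a non-target eye.

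A reader might infer that every early stopper lacks a week-8 score. The documents do not support that: Section 4.4.2 lets subjects who remain for safety evaluation follow the visit schedule, which includes week-8 staining. A reader might also infer that an adjusted interval can never be recovered from the published results. That is wrong whenever the three SDs and the means are reported by arm.

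**Conclusion.** The point holds as a minor one. The plan promises a treatment effect size and does not say what it is. It also sets aside Day 1 data that would narrow the contrast by about 2%, 11% or 5% at assumed correlations of 0.3, 0.5 and 0.7, against the better unadjusted option. These figures assume equal SDs and 12 per arm.

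Endpoint 3 can be calculated in more than one way. The spreads shown (33% to 50%, and 43% to 57%) rest on assumed counts. With no zero-score eyes and no missing scores there would be no spread.

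It would be too strong to read this as a flaw in the trial's main result or as a case for hypothesis tests. The primary endpoint is tolerability, every endpoint discussed here is exploratory, and a confidence interval needs no test.

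**What to change.** Before unblinding, amend Sections 3.4 and 7.2.

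1. **Effect size.** Keep the exclusion of hypothesis tests. In the intention-to-treat set, report the IVIG minus saline week-8 difference adjusted for the Day 1 value, with a 95% interval and no p-value.
   - Do this per subject for OSDI and symptom intensity, and in the target eye for Schirmer I, VBR redness, keratograph redness and NIK BUT. Name one VBR summary (it is graded nasally and temporally) and one NIK BUT measure (first or average) in advance.
   - Beside each, give by arm the unadjusted means and SDs and the number of missing week-8 values. Give also the residual SD and the baseline to week-8 correlation, both of which the next sample size calculation can use.
   - Show the corneal score this way only with its medians and a caution about scores near zero. Leave the other endpoints descriptive.
   - Label all intervals descriptive and not adjusted for multiplicity.
2. **Endpoint 3.** Define it as corneal score 0 at week 8 among target eyes with a Day 1 corneal score above 0, and report the non-target eye separately. In the intention-to-treat set, count a missing week-8 score as not cleared, with the observed-only proportion beside it. Report the numbers of Day 1 zero-score eyes and of missing scores by arm. Give the between-arm difference with a Newcombe 95% interval.

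The cost is SAP wording and a few lines of SPSS, with no new visits or data. The downsides are one degree of freedom per model (21 instead of 22 at 12 per arm), a smaller denominator for endpoint 3, and several intervals that could be over-read.
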